Oral health is essential to general health and significantly influences the development of children. Dental caries has a high economic and social impact due both to the costs associated with its treatment as well as the societal cost of days lost in school by children, in the work by their parents and the sequels that remain throughout life (Wadhawan *et al.*, 2003). Also, since caries is associated with excessive sugar intake, it is a predictor of risk for cardiovascular disease and diabetes in children and adults. The aetiology of early childhood caries (ECC) is complex and the main associated factors are high sugar consumption and inadequate oral hygiene (Leong *et al.*, 2013). The traditional operative treatment of carious lesions often fails, especially when tooth restoration is performed at an early age (Raedel *et al.*, 2017). Less invasive caries treatment strategies have been proposed that would have the advantage of lowering the costs of care as well as decreasing the number of tooth extractions (Stephenson *et al.*, 2010). Fluoride applications are effective in decreasing the incidence of early childhood caries (Gao *et al.*, 2016) while SDF is effective in arresting the progression of cavitated lesions (Duangthip *et al.*, 2017). However, a usual adverse effect of SDF is that it stains the teeth black. New formulations have appeared that replace silver with copper (Tiefenfluorid), to avoid this. At this moment, the effectiveness of Tiefenfluorid to arrest carious lesions in permanent teeth is proven (Thneibat *et al.*, 2008), but there are no studies in deciduous dentition, or clinical studies comparing the effectiveness of all those non-invasive treatments. Also, there is a gap in knowledge about which protocols are most effective and how the interval between application influences clinical effectiveness (Slayton *et al.*, 2018). To date, it is known that a bi-annual application is better than one application per year, but other application protocols have not been studied (Crystal *et al.*, 2017). Due to the mechanisms of enamel and dentin remineralisation, this is a process where maximum fluoride concentration with maximum application frequency can provide the best results. A new six-arm clinical trial could provide important information on the efficacy, cost-effectiveness and potential side-effects of these methods for patients.

Study design and settings

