This study is a randomised, double-blinded, superiority clinical trial with six parallel groups. The hypothesis tested to evaluate two early childhood tooth caries treatment methods with two different application protocols, comparing a placebo, will be performed at the Rīga Stradiņa University's (RSU) Institute of Stomatology Children's Dentistry department.

Participants

According to the AAPD's (American Academy of Pediatric Dentistry) definition of severe early childhood caries (S-ECC) is a condition when a child up to 3 years old has at least one caries damage without cavitates and from 3 to 5 years old with at least one caries damage with cavitates (AAPD). Every week approximately 15 children ages 2-6 years-old with multiple caries damage seek consultations about the possibility to receive planned tooth treatment under general anaesthesia (GA) at the RSU Institute of Stomatology. After confirmation of the diagnosis, the children are put on a waiting list for treatment, which lasts 12 months. These children are offered to participate in this study, while they wait for rehabilitation with general anaesthesia. Every day approximately 10 children arrive that are at an age to be included in the study, with acute pain or an infection. They are also given the opportunity to participate in the study, if they conform with the criteria. As a result, the patient's involved in the study have common characteristics: multiple caries damage with cavities (indicating restorative treatment); a high level of caries risk factors; possible difficulties with behavioural control. To bring the study's sample patients as close as possible to the overall children's population, participants will be included according to defined criteria.

Inclusion criteria:

- children aged 2-6;
- have at least one active caries damage with cavitates (comply with the diagnosis of S-ECC);
- wish to participate in the study;
- parents agree to participation in the study and sign a consent form.

Exclusion criteria:

- the child arrives with an adult who doesn't have the right to sign a consent form, and the person responsible for the child cannot be present;
- chronic or serious acute general illness;
- in the last month has used medications, that could affect the secretion of saliva;
- previously received treatment with products that have a high level of fluoride concentration.

Sample size calculation

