1. arresting of the lesions – restorative treatment may no longer be necessary, but, in case the child are waiting for treatment under GA, they will not lose their place, and restorative treatment will be offered if parents will still want it because of esthetic reasons;
2. staining of the teeth – when lesion is arrested, damaged dental enamel and dentine often change colour, become darker, and the treatment methods can facilitate that (especially SDF), and therefore the teeth can become unattractive;
3. unpleasant taste during the procedure.

[figure not shown]

Fig 2. Flow chart of the clinical trial.

If the parents agree to the study, they will be assigned an appointment with one of two calibrated examiners, who will again explain the study and in whose presence, they will sign the informed consent form. If the parents for some reason decide not to participate, they can withdraw without any negative consequences. The calibrated specialist will perform a damage progression and activity register (ICDAS, Nyvad criteria) and draw lots with a closed envelope, of which group the patient will be included in (with a color code).

The patient, with information about their group's color goes to another office, where one of four trained dentists and assistants will be working (Intervention staff - IS). They will be informed about the medication to be used in each of the groups. The corresponding treatment method will be applied, and the child will be asked to describe their feelings during the procedure by using visual

analogue scale (VAS), the next visit will be set according to the group's corresponding protocol. On all future treatment appointments, the patient will only see the dentists and assistants of IS.

After the last application foreseen in the protocol, the patient will be assigned a control appointment, which will be 12 months after the first examination. During the control appointment one of the calibrated examiners will perform a documentation of stage and activity of carious lesions, not knowing which treatment had been applied. The questionnaires for the parents and children about their satisfaction with the appearance of their teeth will be applied.

Interventions

Patients who agree to participate in the study, will be randomly placed into one of six groups:

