- 4) the level and development of the caries damage and activity (ICDAS, Nyvad criteria).

Outcome measures:

- I. Primary outcome measures:
 - A. Pain history during the observation period, assessed as Yes/No at 12 months follow-up visit.
 - B. Abscess history during the observation period, assessed as Yes/No at 12 months follow-up visit.
 - C. The number of newly extracted or otherwise surgically treated teeth during the observation period, assessed as a number of extracted teeth during the last year at 12 months follow-up visit.
- II. Secondary outcome measures:
 - A. The change in the overall activity of caries as Active/Non-active, assessed at 12 months follow-up visit.
 - B. The progression and change of activity of every lesion, assessed by ICDAS (for progression) and Nyvad (for activity) criteria, at 12 months follow-up visit.
 - C. The parent’s satisfaction with the way their children’s teeth look, assessed by questionnaire, asking: “Are you satisfied with the way your child’s teeth look?”

- and “Would you agree to repeat the treatment procedure used?”, both measurements in 5-point Likert scale, assessed at 12 months follow-up visit.
- D. The child’s satisfaction with their teeth, measured by the visual analogue scale (VAS) with 3 points - happy, not sure, sad, assessed at 12 months follow-up visit.
 - E. The child’s feelings during the treatment, measured by the modified Wong-Baker scale with 3 options - no hurt, hurts a little, hurts a lot), assessed during every appointment (depending on treatment group can be assessed at baseline, 1, 2, 3 weeks and 12 months; or at baseline, 6 and 12 months).
 - F. The direct costs of the treatment and the cost-effectiveness, calculated as EUR spent per treatment protocol; EUR per prevented major complications (in patient-level - pain, abscess, extraction) and EUR per prevented minor complications (in tooth-level - progression of caries lesion), the calculation will be made at 12 months follow-up.
 - G. The treatment method’s undesirable side effects, assessed by parents’ questionnaire at the 12 months follow-up visit.

Statistical analysis

Data will be digitized, by entering in an ad-hoc form in the Google Docs programme. Further the data will be exported cvs (comma separated values) to an archive. Missing data will be eliminated from the analyses, marking them NA.

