4. **WP4** Clinical trial. **The objective of WP4** is to perform the clinical trial according to an established protocol and the highest ethical standards with the primary aim of finding out which high-concentration fluoride application method and which application protocol more effectively protects pre-school children from complications arising from early childhood dental caries. Secondary objectives are to evaluate at which stage of development (cariou lesions) the methods are the most effective; which fluoride application method and protocol is more effective in arresting non-cavitated and cavitated cariou lesions in preschool children; how satisfied are parents and patients with SDF and Tiefenfluorid application procedures and side-effects (staining) and what are the costs and cost-effectiveness of each method and application protocol.
 1. Enrolment of patients in the study. General staff will offer suitable patients the chance to register for the procedures. A calibrated examiner (postdoctoral researcher) will inform parents about all details of the study. If the offered is accepted, parents sign the informed consent form.

2. Initial examination and interviewing of enrolled patients and their parents by a calibrated examiner (postdoctoral researcher).
3. Random allocation in six intervention groups. This will be done by a calibrated examiner (postdoctoral researcher) using six closed envelopes containing colour codes.
4. Performing interventions according to the protocol of each study group. Those interventions will be done by Intervention Staff (IS) - four trained postgraduate students and assistants (dental hygiene students).
5. Performing and documenting emergency treatment during the follow-up period. Done by trained general staff on a daily basis according to patient needs. Registration will be done using a pre-prepared form.
6. Follow-up examination. Done by calibrated examiner (postdoctoral researcher).

Deliverables of WP4

D4.1 Enrolment registration form.

D4.2 Signed informed consent forms.

D4.3 Initial patient examination forms (including parent questionnaire).

D4.4 Intervention registration forms (including Visual Analogue Scale [VAS] of patient satisfaction).

D4.5 Emergency treatment forms (including VAS of patient satisfaction).

D4.6 Follow-up examination forms (including VAS of patient acceptance and Likert scale questions of parents acceptance).

Milestones of WP4

MS4.1 Meetings about enrollment, randomization and allocation.

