 - a. Patients received treatment outside the RSU Institute of Stomatology – every case will be analysed separately; if, for any reason, the patient attended a dentist who was not trained for the study (in the Institute of Stomatology or in another dental clinic), the recordings of treatment performed will be analysed – if there is no doubt regarding the information gained and if the treatment was done according to the guidelines used in the study, the patient will be kept in the study. In case of doubt, he/she will be excluded from analysis. This increases the risk of loss of follow-up, but it is important that we are sure about the impact of the treatment performed. Evenmore, as described above, we will include more patients than required to assure the study power even after some losses of follow-up.
 - b. Blinded research team members are informed about colour codes of the treatment groups – we will consider changing the person in case the this knowledge leads to performance or detection bias. We also will include as less personal as possible and the most motivated colleagues to avoid such errors.
 - c. Patients find out which treatment group they have been assigned to– it is possible that the groups which receive SDF “feel” the treatment to be more effective because of the staining side effect. However, we are not yet sure how important this effect will be, as all of those children have tooth damage which includes some colour change of the lesions. It is also known that arrested lesions tend to become darker even without the application of any agent. We will be able to address this risk by evaluating the patient and parent satisfaction in different treatment groups.

Infrastructure

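### The double-blind label does not fit the SDF arms: operators know the product and staining can reveal it, which leaves the 12-month pain and abscess histories open to reporting bias; side effects are asked about only at 12 months

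*Protocol*

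**What the plan says.** Study design and settings: "This study is a randomised, double-blinded, superiority clinical trial with six parallel groups".

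Randomization, allocation and blinding describes the operators and the family: "The patient, with information about their group's color goes to another office", and of the treating staff, "They will be informed about the medication to be used in each of the groups". The same section says that the 12-month examiner does not know which treatment was applied. It also has parents told in advance that teeth may darken, naming SDF in particular. The introduction says: "However, a usual adverse effect of SDF is that it stains the teeth black". Tiefenfluorid is presented there as a formulation intended to avoid this.

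Under Outcome measures, primary outcome I.A is "Pain history during the observation period, assessed as Yes/No at 12 months follow-up visit". I.B has the same form for abscess. I.C counts teeth extracted or otherwise surgically treated. Side effects (II.G) are collected by a parents' "questionnaire at the 12 months follow-up visit". The child's feelings during treatment (II.E) are recorded at each appointment.

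Risks 2c accepts that SDF families may feel that their treatment works better because of the stain, and answers: "We will be able to address this risk by evaluating the patient and parent satisfaction in different treatment groups".

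WP4 also produces a record made during follow-up, D4.5: "Emergency treatment forms (including VAS of patient satisfaction". The protocol does not name it as a source for any primary outcome.

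**The concern.** A double-blind label tells readers that neither the family nor the assessor can let knowledge of the treatment colour the outcome. In the SDF arms the design cannot guarantee that for either party. This matters most for outcomes that depend on what someone reports, and pain and abscess history are of that kind. If families who recognise SDF report more or fewer events than placebo families with the same experience, a primary comparison shifts with no difference in disease.

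The protocol recognises the risk but offers a response that does not act on it. A satisfaction score measures opinion of the teeth and the procedure. It neither measures nor corrects error in a pain or abscess report.

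The side-effect outcome has a separate timing problem. A single question at 12 months comes at different distances from treatment in the two schedules, and choosing between schedules is part of the trial's primary aim (WP4).

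**Working it through.** **Who can know what.** The protocol's statements, party by party:

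| Party | What the protocol says | Consequence |
|---|---|---|
| Operators | Told the product for each group | Not blind |
| Families | Know the colour; warned of darkening, especially with SDF; SDF stains black | SDF can be recognised |
| 12-month examiner | Not told the treatment, but examines the teeth | SDF can be recognised |
| Families, as to schedule | Two visits six months apart or four weekly visits; no dummy visits described | Schedule is known, but each schedule has its own placebo arm, so product is not revealed |
| Families and examiner, Tiefenfluorid arms | Described as avoiding the black stain | Less exposed to unmasking against placebo |

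The exposure is therefore concentrated on comparisons that involve SDF.

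**Which outcomes are exposed.** I.A and I.B are histories with no stated informant. The children are aged 2 to 6, so a parent is the likely source; this is an inference. I.C, a count of treated teeth, depends less on recall.

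**How large could the bias be?** The protocol gives no figure for differential reporting, so this is an illustration on assumed values. Inputs: a 30% rate in both arms (the planning rate for complications of all kinds in the placebo groups, borrowed here for a single outcome); no true effect; 49 per group (the stated requirement); a fraction s of events reported under SDF and all events reported under placebo; and the power formula in Fig 1.

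For s = 0.75:
- Apparent SDF rate: 0.30 × 0.75 = 0.225. Spurious difference: 7.5 points, against a planned 20 (7.5/20 = 37.5%).
- Standard error: √[(0.30×0.70 + 0.225×0.775)/49] = 0.0886. z = 0.075/0.0886 = 0.847.
- Two-sided α = 0.05: Φ(0.847 − 1.960) + Φ(−0.847 − 1.960) = 0.133 + 0.0025, about 13.5%.
- α = 0.05/9 (the nine planned comparisons): Φ(0.847 − 2.773) + Φ(−0.847 − 2.773), about 2.7%.

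Chance of a false significant difference over a range of s:

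| s | Apparent SDF rate | α = 0.05 | α = 0.05/9 (nominal 0.56%) |
|---|---|---|---|
| 1.0 | 30% | 5.0% | 0.56% |
| 0.9 | 27% | 6% | 0.8% |
| 0.8 | 24% | 10% | 1.8% |
| 0.75 | 22.5% | 13.5% | 2.7% |
| 0.7 | 21% | 18% | 4.1% |
| 0.5 | 15% | 44% | 16.7% |

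This table takes one direction only, the one that Risks 2c suggests. Parents unhappy with stained teeth might report more, which would bias against SDF.

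**Side-effect timing.** Take the first application as week 0 and the control visit as week 52.
- Weekly arms: applications at weeks 0, 1, 2 and 3. Last application to question: 52 − 3 = 49 weeks.
- Six-month arms: applications at weeks 0 and 26. Last application to question: 52 − 26 = 26 weeks.
- Gap between schedules: 49 − 26 = 23 weeks.

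Within a schedule, each product and its placebo have the same interval, so that comparison is not confounded by timing.

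**The case against.** The strongest reply has five parts.

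- **Meaning of the label.** Double-blind can mean family and examiner, and the protocol is open about operators knowing the product. That stands: operator knowledge alone does not contradict the label. It does not rescue the label in the SDF arms, where the stain is visible to both of those parties.
- **Staining is not specific to SDF.** Risks 2c notes that these children already have discoloured lesions and that arrested lesions darken without any agent. This makes unmasking less certain. It does not make blinding secure, because the protocol itself attributes black staining to SDF and warns parents of it.
- **Source of the primary outcomes.** A reader might infer that pain and abscess rest on parents' recall as a matter of protocol. The text does not say so. It names no informant, and the emergency registration could feed the history. The attached forms, which might settle this, are not part of the text at hand. What stands is that the source is not fixed.
- **Schedule.** A reader might also infer that seeing the schedule breaks the blind to product. It does not, since each schedule has a placebo arm.
- **Emergency records as the primary source.** It is tempting to say that they should replace the history. They would miss pain managed at home, they also depend on parents who seek care and may have guessed the product, and Risks 2a expects some treatment elsewhere. Replacement is a debatable trade-off.

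On side effects, II.E already captures hurt at each appointment, and staining can still be seen at 12 months. The loss therefore concerns other transient effects, such as the unpleasant taste that parents are told to expect.

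**Conclusion.** The point holds, limited as follows. The protocol claims a blinding property that the design cannot secure for the SDF arms. SDF comparisons on pain and abscess history are open to reporting bias of unknown size and direction, and the stated safeguard does not address it. Tiefenfluorid versus placebo is less affected, and extraction counts depend less on recall.

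The size is illustrative. With one in four SDF events unreported, the apparent difference is 7.5 points, and the false-positive chance is about 13.5% at α = 0.05 or 2.7% at 0.05/9 (nominal 0.56%). Both rest on an assumed reporting fraction, a borrowed 30% rate and a single direction. They show that modest differences in reporting could matter; they are not evidence that such bias will occur or that it would favour SDF.

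The timing gap of about 23 weeks follows from the schedules. It affects only the between-schedule comparison of side effects. The late single question is also likely to under-record transient effects in every arm.

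**What to change.** 1. **Blinding statement.** Replace the double-blind label with a statement that operators are not blind, that families and the 12-month examiner are not told the product, and that SDF staining may unmask both. In Risks 2c, withdraw the claim that satisfaction scores address this risk. Cost: wording only.
2. **Side effects.** Record them at every application visit on the existing intervention registration form (D4.4), and keep the 12-month questionnaire as a supplement. Cost: one added form item. The number of visits still differs by schedule, so schedules will have unequal opportunities to report.
3. **Pain and abscess.** Keep the 12-month history as primary and say who gives it. Add a supportive analysis of pain, abscess and extraction events taken from the emergency treatment forms and dental records already collected, stating that these miss home-managed pain and also depend on parents seeking care. Cost: abstracting and coding existing records. Agreement between the two sources would strengthen an SDF result; disagreement would warn against over-reading it.

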Data will be exported in the statistics programme R (R Core Team, 2013), and program packages Tidyverse (Wickham, 2017) un Lubridate (Grolemund and Wickham, 2011) will be used for data processing.

Ethics

The study will be performed in accordance with the Helsinki Declaration (World Medical Association, 2013), and will observe personal data protection.

The patient will be offered to voluntarily choose, whether to participate in the study, ensuring, that if they decline, they will receive the same quality conventional treatment. The patients involved will be the ones that are waiting in line for state-funded restorative caries treatment under general anaesthesia, therefore, the possibility to participate in the study can be viewed as an additional treatment, which the children can receive during the waiting period. All the patients – both those that

participate in the study, as well as those who decline, if during the waiting period an emergency situation arises which requires immediate intervention, it will be ensured according to standard protocol at the Institute of Stomatology Children's Dentistry department.

In the attachment you can find the parent's informed consent form (1st attachment), a questionnaire for the children (2nd attachment), a description of acute aid form (3rd attachment) and a clinical examination form (4th and 5th attachment). Using ad hoc, the forms data will be digitized, entering the data anonymously and ensuring, that patients cannot be identified from the stored data.

Safety

The medications used are registered for use in professional caries treatment:

1. Riva Star SDF (35-40% silver fluoride, 15-20% ammonium) (SDI Limited, 2015);
2. Tiefenfluorid (0,4% $\text{CuSiF}_6 \times 6 \text{H}_2\text{O}$, 10,9% $\text{MgSiF}_6 \times 6 \text{H}_2\text{O}$, 0,1% NaF, 9,6% $\text{Ca}(\text{OH})_2$) (Knappwost-Gieseke, 2002).

Work packages

Work breakdown structure can be seen in Fig 3.

[figure not shown]

Fig 3. Work packages of the clinical trial.

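### Primary outcome C does not separate extractions in planned general-anaesthesia care from complication-driven ones, although the waiting list and the follow-up both run 12 months

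*Protocol*

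**What the plan says.** **Waiting list.** Protocol, Participants: "After confirmation of the diagnosis, the children are put on a waiting list for treatment, which lasts 12 months". The same section adds: "These children are offered to participate in this study, while they wait for rehabilitation with general anaesthesia". Under Randomization, allocation and blinding, parents are told that "in case the child are waiting for treatment under GA, they will not lose their place".

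**Follow-up.** The same section sets a "control appointment, which will be 12 months after the first examination". That first examination takes place at a separate appointment, after the family has been approached and has agreed.

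**Outcome.** Primary outcome C, under Outcome measures, is the number of teeth newly extracted or otherwise surgically treated in the observation period, "assessed as a number of extracted teeth during the last year at 12 months follow-up visit". No indication is named. Secondary outcome F then lists extraction with pain and abscess as a major complication at patient level.

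**Who is enrolled.** Participants names a second source, children who arrive with acute pain or infection: "They are also given the opportunity to participate in the study, if they conform with the criteria". That section does not say they are on the GA list. Ethics describes the participants differently: "The patients involved will be the ones that are waiting in line for state-funded restorative caries treatment under general anaesthesia".

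**Related provisions.** The Work packages include a form for emergency treatment given during the study, but outcome C does not refer to it. Under Risks, treatment by a dentist not trained for the study is reviewed case by case, and doubtful cases leave the analysis.

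**The concern.** Outcome C is meant to show failure of caries control. An extraction done because a child's turn on a list has come up is not such a failure, yet the definition admits it. The list and the follow-up have the same nominal length, so the two can coincide around the visit at which the outcome is read.

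Two things are at stake. First, a primary outcome may mix two kinds of event, and its difference between arms may shrink or be biased. Second, secondary outcomes A and B need lesions that can still be examined. A lesion restored or extracted under GA before the visit can no longer show whether it progressed or arrested. This second problem arises even if GA is purely restorative.

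**Working it through.** **1. Order of dates for a listed child.**

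- GA due = listing + 12 months (Participants).
- Control visit = first study examination + 12 months (Randomization, allocation and blinding).
- Listing comes before the first examination, because children are approached while already waiting.

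Subtracting, GA due − control visit = listing − first examination, which is zero or negative. On the stated figures GA falls due at or before the visit, earlier by the gap between listing and examination. The Protocol does not give that gap, and the actual GA date may differ from the due date.

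**2. What outcome C does with a planned extraction.** The definition has no limit by indication, setting or urgency. An extraction under GA within the year meets it as written.

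**3. The plan's own figures.** Sample size calculation assumes complications in 30% (placebo) and 10% (treatment), α = 0.05, 80% power and τ = 9 comparisons, and states 49 children per group. The printed formula gives

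n = (0.3 × 0.7 + 0.1 × 0.9) × ((2.773 + 0.842) / 0.20)² = 97.99, so 98 per group.

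The stated 49 is half of this. That is a separate matter and the present point does not depend on it. Power is shown at both sizes below only because of it.

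**4. Effect on the event rate.** Let g be the share of an arm with a planned GA extraction before the visit, independent of true complications. The observed rate is p + (1 − p)g. The Protocol does not give g, so every value here is an assumption. Power uses the Protocol's second formula with τ = 9.

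| g placebo | g treatment | Placebo | Treatment | Difference | Power, 49 per group | Power, 98 per group |
|---|---|---|---|---|---|---|
| 0 | 0 | 30% | 10% | 20 points | 41% | 80% |
| 10% | 10% | 37% | 19% | 18 points | 23% | 54% |
| 20% | 20% | 44% | 28% | 16 points | 14% | 34% |
| 20% | 10% | 44% | 19% | 25 points | 50% | 87% |
| 10% | 20% | 37% | 28% | 9 points | 4% | 8% |

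Example: 0.30 + 0.70 × 0.20 = 0.44 and 0.10 + 0.90 × 0.20 = 0.28.

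With equal g the difference shrinks. In the last two rows g differs by arm. The text on expected results and side effects supports either direction: arrest may make restorative treatment unnecessary, while darkened teeth, especially after SDF, may lead parents to want it.

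**5. Limit of the model.** It treats complications as one yes/no proportion, as the sample size section does. Outcome C itself is a count. Pain and abscess are separate primary outcomes, to which a planned extraction adds no event.

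**The case against.** A reader might infer that planned GA extractions will certainly be scored as complications, for many children, and that every comparison will be diluted. The documents do not support this.

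- **Content of GA.** The Protocol calls it rehabilitation or restorative treatment and never says that it includes extractions. A restoration is not an event under outcome C.
- **Sequence.** No text says that GA precedes the visit. Ethics presents the trial as extra treatment during the wait, which can be read as GA coming afterwards. The flow chart, the Gantt chart and the attached forms are not available here and might settle the order or record why a tooth was extracted.
- **Share affected.** Acute attenders are not said under Participants to be listed, so the affected fraction is unknown.
- **Existing rules.** The Risks provision on dentists not trained for the study, which includes dentists at the Institute, could send some GA cases to review or exclusion instead of scoring.
- **Direction.** If arrest reduces GA uptake in the active arms, the difference can widen, as the 44% versus 19% row shows.

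All of this stands against the strong reading. The definition remains open all the same. Nothing in the text excludes a planned extraction or places the visit before GA. The Risks provision does not sort extractions by indication either, and applying it to GA would remove children after randomisation for a reason that may depend on arm.

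**Conclusion.** The point holds in conditional form. For listed children GA can fall due at or before the control visit. Any extraction done then as planned care would count under primary outcome C, and lesions treated under GA would be lost to the progression and activity outcomes.

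The size cannot be fixed from the Protocol. With equal assumed shares of 10% to 20%, the planned 20-point difference falls to 18 to 16 points. With unequal shares of the same size it ranges from 9 to 25 points. These figures rest on the assumed g, on its independence from true complications, and on treating the outcome as a single proportion. Neither dilution nor bias in a particular direction is established.

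The ambiguity sits in a primary outcome and is cheap to remove, so it should be settled. Participants and Ethics also disagree on whether all participants are on the GA list, and must be reconciled.

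**What to change.** 1. Define outcome C as complication-driven extraction or surgical treatment, with the indication taken from the emergency treatment form and clinic records. Report extractions within planned GA care separately.
2. When GA falls before the 12-month visit, do the study follow-up examination before the GA session. GA timing itself stays as it is.
3. Record whether GA was received and its date, and report both by arm.
4. Add a sensitivity analysis of outcome C that counts all extractions.
5. Reconcile Participants with Ethics on who is on the GA list.

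Ending a child's observation at the GA date is not recommended as the main rule. If treatment affects GA uptake, follow-up time would then depend on arm. It could serve as a further sensitivity analysis.

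**Cost.** Two extra data fields (GA date and indication for extraction) and revised outcome wording. Some examinations will take place before 12 months, so follow-up will be slightly unequal. That inequality could itself differ by arm, which is why GA dates should be reported by arm. A complication-driven outcome C will also overlap more with the pain and abscess outcomes.
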